1.3 Schema

The general study design is summarised in Figure 1.

Figure 1. Study design

2. INTRODUCTION

2.1 Study rationale

The Scientific Expert Committee (SEC) of Oncology and Haematology, nominated by Central Drugs Standard Control Organisation (CDSCO), met on 12-Feb-2020. The committee provided recommendations to obtain marketing authorization for Acalabrutinib in the treatment of patients with CLL/SLL, and patients with MCL who have received at least one prior therapy. The marketing authorization was provided with a condition to conduct a phase IV clinical trial as per the requirements in the latest New Drug and Clinical Trial Rules (2019) in India. The phase IV trial will be a part of the marketing authorization condition, which will be issued for the additional indication of CLL for Acalabrutinib in India.

In line with the SEC recommendation and to comply with the marketing authorization condition, the current phase IV study plans to assess the safety and efficacy of Acalabrutinib in Indian patients. The data obtained from the study will help to understand the safety and efficacy profile of Acalabrutinib in Indian patients with CLL/SLL, and patients with MCL who have received at least one prior therapy. The study will add information to currently available safety and efficacy data on Acalabrutinib.

2.2 Background

2.2.1 Acalabrutinib

B cell antigen receptor (BCR) expression is essential for B-cell function, and loss of expression leads to rapid cell death. (Buchner & Müschen, 2014) The BCR over-expression contributes to the majority of B-cell malignancies. Several downstream protein kinases such as BTK (Bruton Tyrosine Kinase) are critical in the BCR signalling cascade. Due to the influence of BTK on cell proliferation and survival, it is an attractive target for inhibition to treat diseases such as CLL and other B-cell lymphomas. (Isaac & Mato, 2020)

Acalabrutinib is a selective small-molecule inhibitor of BTK. BTK is a signalling molecule of the BCR and cytokine receptor pathways. In B cells, BTK signalling results in B-cell survival and proliferation and is required for cellular adhesion, trafficking, and chemotaxis.

Acalabrutinib and its active metabolite, ACP-5862, form a covalent bond with a cysteine residue in the BTK active site, leading to irreversible inactivation of BTK ($IC_{50} \leq 5$ nM) with minimal off-target interactions. In a screen of 380 mammalian wild-type kinases, the only additional kinase interactions at clinically relevant concentrations of Acalabrutinib and ACP-5862 were with BMX and ERBB4, with 3- to 4-fold less potency than BTK. In non-clinical studies, Acalabrutinib inhibited BTK-mediated activation of downstream signalling proteins CD86 and CD69, inhibited malignant B-cell proliferation and survival, and had minimal activity on other immune cells (T cells and Natural Killer cells). (PI, 2020)

In patients with B-cell malignancies dosed with Acalabrutinib 100 mg twice daily, median steady-state BTK occupancy of $\geq 95\%$ in peripheral blood was maintained over 12 hours, resulting in inactivation of BTK throughout the recommended dosing interval.

2.2.2 Chronic Lymphocytic Leukaemia and Small Lymphocytic Lymphoma

CLL and SLL are characterized by a progressive accumulation of leukemic cells in the peripheral blood, bone marrow, and lymphoid tissues. Morphologically, these leukemic cells appear as small, mature lymphocytes that may be found admixed with occasional larger or atypical cells, or pro-lymphocytes. CLL and SLL are different manifestations of the same disease and are managed in much the same way. The major difference is that in CLL, a significant number of the abnormal lymphocytes are found in the peripheral blood in addition to bone marrow and lymphoid tissue, and in SLL, the bulk of disease is in lymph nodes, bone marrow, and other lymphoid tissues, and there are few (if any) abnormal lymphocytes circulating in the peripheral blood. (Wierda et al., 2020)

Chronic lymphocytic leukaemia is a malignancy of B cells that predominantly affects an elderly population. It is the most prevalent form of adult leukaemia, with an age-adjusted incidence of 3.3–6.4 per 100,000 person-years and a median age at diagnosis of 70 years (Noone AM, April 2018). The diagnosis of CLL is established using peripheral blood and immune-phenotyping and requires a minimum of $5 \times 10^9/L$ monoclonal B cells that co-express the surface antigens CD5, CD19, CD20, and CD23. In routine practice, patients with asymptomatic early-stage disease should be monitored without therapy unless they have evidence of disease progression or disease-related symptoms. Treatment of CLL is initiated once there is evidence of progressive or symptomatic/active disease as defined by iwCLL guidelines (Hallek et al., 2018; Hallek et al., 2008). Despite the relatively long life expectancy for early-stage disease, CLL remains an incurable disease.

The incidence of CLL in India is 0.41 per 100,000 person-years not; as common as in the western countries. However, estimates of the incidental cases are 5000 per year with a prevalence of 25000 patients (one-third that of the estimate for the United States). (Lad et al., 2018) In India, CLL accounts for 3-5% of all leukaemia types. CLL is a disease of the elderly and the median age of CLL presentation is >60 yrs in India. The high-risk CLL is defined, at least in part, by a genetic aberration of the TP53 gene [i.e., del(17p) or TP53 mutation]. The incidence of high-risk characteristics (del 17p) increase up to 50% in patients with relapsed and refractory CLL (Gogia et al., 2019). An Indian study showed that high-risk cytogenetic abnormalities like del(17p) and

del(11q) were seen in 13.3% patients, which are more common in India than that reported in the West. (Saxena et al., 2016)

The safety and efficacy of Acalabrutinib in previously untreated CLL were evaluated in a randomised, multi-centre, open-label Phase 3 study (ELEVATE-TN) of 535 patients. Patients received Acalabrutinib plus Obinutuzumab, Acalabrutinib monotherapy, or Obinutuzumab plus Chlorambucil. Patients 65 years of age or older or between 18 and 65 years of age with coexisting medical conditions were included in ELEVATE-TN. The trial also allowed patients to receive antithrombotic agents other than warfarin or equivalent vitamin K antagonists. (PI, 2020)

Patients were randomised in a 1:1:1 ratio into 03 arms to receive

- Acalabrutinib plus Obinutuzumab (Acalabrutinib+G): Acalabrutinib 100 mg was administered twice daily, starting on Cycle 1 Day 1 until disease progression or unacceptable toxicity. Obinutuzumab was administered starting on Cycle 2 Day 1 for a maximum of 6 treatment cycles. Obinutuzumab 1000 mg was administered on Days 1 and 2 (100 mg on Day 1 and 900 mg on Day 2), 8 and 15 of Cycle 2 followed by 1000 mg on Day 1 of Cycles 3 up to 7. Each cycle was of 28 days.
- Acalabrutinib monotherapy: Acalabrutinib 100 mg was administered twice daily until disease progression or unacceptable toxicity.
- Obinutuzumab plus Chlorambucil (GClb): Obinutuzumab and Chlorambucil were administered for a maximum of 6 treatment cycles. Obinutuzumab 1000 mg was administered on Days 1 and 2 (100 mg on Day 1 and 900 mg on Day 2), 8 and 15 of Cycle 1 followed by 1000 mg on Day 1 of Cycles 2 up to 6. Chlorambucil 0.5 mg/kg was administered on Days 1 and 15 of Cycles 1 up to 6. Each cycle was of 28 days.

Patients were stratified by 17p deletion mutation status (presence versus absence), ECOG performance status (0 or 1 versus 2), and geographic region (North America and Western Europe versus other). After confirmed disease progression, 45 patients randomised on the GClb arm crossed over to Acalabrutinib monotherapy.

The primary endpoint was progression-free survival (PFS) as assessed by an Independent Review Committee (IRC) per iwCLL 2008 criteria with the incorporation of the clarification for treatment-related lymphocytosis (Cheson 2012). With a median follow-up of 28.3 months, PFS by IRC indicated a 90% statistically significant reduction in the risk of disease progression or death for previously untreated CLL patients in the Acalabrutinib + G arm compared to the GClb arm. At the time of analysis, median overall survival had not been reached in any arm with a total of 37 deaths: 9 (5%) in the Acalabrutinib +G arm, 11 (6.1%) in the Acalabrutinib monotherapy arm, and 17 (9.6%) in the GClb arm.

PFS results for Acalabrutinib with or without Obinutuzumab were consistent across subgroups, including high-risk features in the high-risk CLL population (17p deletion, 11q deletion, TP53 mutation, and un-mutated IGHV), the PFS hazard ratios of Acalabrutinib with or without Obinutuzumab versus Obinutuzumab plus Chlorambucil were 0.08 [95% CI (0.04, 0.15)] and 0.13 [95% CI (0.08, 0.21)], respectively.

Patients with CLL who received at least one prior therapy (PI, 2020)

The safety and efficacy of Acalabrutinib in relapsed or refractory CLL were evaluated in a randomised, multi-centre, open-label phase 3 study (ASCEND) of 310 patients who received at

least one prior therapy. Patients received Acalabrutinib monotherapy or Investigator's choice of either Idelalisib plus Rituximab or Bendamustine plus Rituximab. The trial allowed patients to receive antithrombotic agents other than warfarin or equivalent vitamin K antagonists.

Patients were randomised 1:1 to receive either: Acalabrutinib 100 mg twice daily until disease progression or unacceptable toxicity, or Investigator's choice:

- Idelalisib 150 mg twice daily until disease progression or unacceptable toxicity in combination with ≤ 8 infusions of rituximab ($375 \text{ mg/m}^2/500 \text{ mg/m}^2$) on Day 1 of each 28-day cycle for up to 6 cycles
- Bendamustine 70 mg/m^2 (Day 1 and 2 of each 28-day cycle) in combination with rituximab ($375 \text{ mg/m}^2/500 \text{ mg/m}^2$) on Day 1 of each 28-day cycle for up to 6 cycles

Patients were stratified by 17p deletion mutation status (presence versus absence), ECOG performance status (0 or 1 versus 2), and a number of prior therapies (1 to 3 versus ≥ 4). After confirmed disease progression, 35 patients randomised on the Investigator's choice of either Idelalisib plus Rituximab or Bendamustine plus Rituximab crossed over to Acalabrutinib.

The primary endpoint was PFS as assessed by IRC iwCLL 2008 criteria with the incorporation of the clarification for treatment-related lymphocytosis (Cheson 2012). With a median follow-up of 16.1 months, PFS indicated a 69% statistically significant reduction in the risk of death or progression for patients in the Acalabrutinib arm. At the time of analysis, median overall survival had not been reached in any arm with a total of 33 deaths: 15 (9.7%) in the Acalabrutinib monotherapy arm and 18 (11.6%) in the Investigator's choice of either Idelalisib plus rituximab or Bendamustine plus rituximab arm.

PFS results for Acalabrutinib were consistent across subgroups, including high-risk features. In the high risk CLL population (17p deletion, 11q deletion, TP53 mutation, and un-mutated IGHV), the PFS HR was 0.27 [95% CI (0.17, 0.44)].

2.2.3 Mantle Cell Lymphoma

MCL is a distinct sub-type of non-Hodgkin's lymphoma (NHL) comprising approximately 7% of all adult NHL, with a moderately aggressive clinical course and poor outcome. The primary cell of origin of MCL is thought to be a naive B cell of pre-germinal centre origin within the mantle zone of the lymph node. The incidence of MCL increases with age and an increase in incidence has been observed over time. (Zhou et al., 2008) The disease is characterized by the chromosomal translocation $t(11;14)(q13\cdot3; q32\cdot33)$, resulting in over-expression of the cell cycle protein cyclin D1. (McKay, Leach, Jackson, Robinson, & Rule, 2018) the role of BTK inhibitors was demonstrated to manage relapse and refractory cases of MCL. (Schieber, Gordon, & Karmali, 2018)

The safety and efficacy of Acalabrutinib in MCL were evaluated in an open-label, multi-centre, single-arm Phase 2 study (ACE-LY-004) of 124 previously treated patients. All patients received Acalabrutinib 100 mg orally twice daily until disease progression or unacceptable toxicity. The trial did not include patients who received prior treatment with BTK inhibitors. The primary endpoint was Investigator-assessed overall response rate (ORR) per the Lugano classification for non-Hodgkin's lymphoma (NHL). Duration of Response (DoR) was an additional outcome measure. (PI, 2020)

The median age was 68 (range 42 to 90) years, 79.8% were male, and 74.2% were Caucasian. At baseline, 92.8% of patients had an ECOG performance status of 0 or 1. The median time since diagnosis was 46.3 months, and the median number of prior treatments was 02 (range 1 to 5), including 17.7% with prior stem cell transplant. The most common prior regimens were CHOP-based (51.6%) and ARA-C (33.9%). At baseline, 37.1% of patients had at least one tumour with the longest diameter ≥ 5 cm, 72.6% had extra-nodal involvement, including 50.8% with bone marrow involvement. The simplified Mantle Cell Lymphoma International Prognostic Index (MIPI) score, (which includes age, ECOG score, and baseline lactate dehydrogenase and white cell count) was intermediate in 43.5% and high in 16.9% of patients. (PI, 2020)

As per recommendation by the Regulatory Authority, the current phase-IV study is planned with the aim to assess the safety and efficacy of Acalabrutinib in Indian patients as a post-marketing requirement. The data obtained from the present study will help to understand the safety and efficacy profile of Acalabrutinib in Indian patients with CLL and MCL.

2.3 Benefit/risk assessment

Patients with CLL/SLL and patients with MCL who have received at least one prior therapy will be treated with Acalabrutinib 100 mg BID from Day1 Cycle 1 for 06 cycles (each treatment cycle is 28 days). During this time, the patient will be monitored for safety and efficacy according to the assessment frequency presented in Table 1. The efficacy and safety of Acalabrutinib is established in various studies in CLL/SLL and MCL patients (refer Section 2).

Overall, Acalabrutinib monotherapy demonstrated satisfactory safety profile in various studies conducted in patients of CLL/SLL, and MCL (Table 3). Most AEs are low-grade (Grade 1 to 2) with relatively few related high-grade (Grade 3 to 4) AEs.

More detailed information about the known and expected benefits and risks and reasonably anticipated AEs of Acalabrutinib may be found in the Acalabrutinib India PI.

3. OBJECTIVES AND ENDPOINTS

Table 2: Study objectives

Primary objective	Outcome measures
To investigate the safety of Acalabrutinib among patients with CLL/ SLL, and relapsed & refractory MCL in Indian patients	Adverse Events (AEs), Serious Adverse Events (SAEs), and AEs of Special Interest (AESI) including Arrhythmias (Atrial Fibrillation), Anaemia, Hypertension, Bleeding, Infections, Reasons for discontinuation and second primary malignancies
Secondary objectives	Secondary Outcome measures

To assess the efficacy of Acalabrutinib in Objective response to treatment.
patients of CLL/SLL and relapsed &
refractory MCL in Indian patients

Patient-reported outcome (PRO)

Health related quality of life (EORTC QLQ-C30 Questionnaire)

4. STUDY DESIGN

4.1 Overall design

The study is a phase IV, open-label, single-arm, multi-centre, prospective study to be conducted in India. The study will evaluate the safety and efficacy of Acalabrutinib in Indian adult patients with CLL/SLL, and patients with MCL who have received at least one prior therapy. The Investigator will be trained on the locally approved Prescribing Information before the enrolment of the first patient at their site to ensure compliance and proper dosing of the study drug. Patients will be monitored throughout the study period for AEs /SAEs/AESI of Acalabrutinib.

Patients with CLL/SLL and MCL who are eligible to receive Acalabrutinib treatment as per locally approved prescribing information and ratified by an independent clinical judgment of treating physician, will be evaluated for inclusion into the current phase IV trial. To enrol approximately 100 patients into the study, it is expected that approximately 150 patients will need to be screened.

The study will be initiated after approval by the Ethics Committee. Patients will undergo the following phases: Screening/Enrolment Phase, Treatment Phase, and Follow-up Phase.

[figure not shown]
The decision of patients to participate in this study must not, in any way, impact the standard of care they are receiving or any benefits to which they are otherwise entitled. Prior to data collection, all patients must sign an ICF, allowing for data collection and source data verification to be performed in accordance with local requirements and Sponsor policy.

Two cohorts of patients will be included in the current study (a) patients with CLL/SLL who are treatment naïve or have received at least one prior therapy (N= 90) and (b) patients with MCL who have received at least one prior therapy (N= 10). Potential patients will undergo screening phase within 07 days prior to the first Acalabrutinib dose. Patients who meet the protocol-defined inclusion/exclusion criteria will be prospectively enrolled into the study.

Acalabrutinib capsules 100 mg administered orally twice daily (BID) for 06 cycles, starting from Cycle 1, Day 1, and continuing up to Cycle 6, Day 28; or until study drug discontinuation due to either disease progression or, unacceptable toxicity, or other reasons, whichever occurs earlier.

Acalabrutinib will be provided by the Sponsor to patients in the Treatment Phase. The Sponsor shall also conduct laboratory investigations for safety and efficacy evaluation, including haematology, biochemistry, radiology, and electrocardiography (ECG), as mentioned in the SoA table.

Figure 2: Study Flow

4.1.1 Screening Phase (Visit 1)

Patients, or their Legally Acceptable Representative (LAR), will provide written informed consent before any trial-specific procedures are performed. If the patient and/or LAR are unable to read, an impartial witness should be present during the entire informed consent discussion. During the Screening Phase, eligibility criteria will be reviewed, and a complete clinical evaluation will be performed as specified in the SoA (Table 1). Screening procedures will be performed up to 07 days prior to Cycle 1, Day 1. All baseline disease characteristics will be captured based on the evaluation performed as a part of routine clinical practice. The investigations that are required before the consideration of the patient for Acalabrutinib treatment must have been performed before the first dose (Cycle 1, Day 1). The NGS tests should be performed before the start of the treatment as per SoA (Table 1). Next-generation sequencing will be conducted to understand the genetic profile in Indian settings. Molecular cytogenetics (FISH) for del(13q), del(11q), del(17p), trisomy 12 in peripheral blood lymphocytes; TP53 mutation; immunoglobulin variable heavy chain (IGHV) mutational status will be assessed before the start of treatment in CLL/SLL-naïve patients, or CLL/SLL patients who did not have their report. However, MCL patients are Relapsed/Refractory and their previous report data will be used. A six months old report can be considered for both the conditions.

4.1.2 Treatment Phase (Visit 2 To 7)

The Treatment Phase will start from Cycle 1, Day 1 to Cycle 6, Day 28, or until study drug discontinuation due to either disease progression, unacceptable toxicity; or other reasons, whichever occurs earlier. Each cycle of treatment is defined as 28 days of twice-daily Acalabrutinib treatment.

Details of the procedures performed during the Treatment Phase are outlined in the Schedule of Activity table. Patients will be closely monitored for adverse events and other safety evaluations, including laboratory investigations, concomitant medications etc. as provided in SoA table. If disease progression is diagnosed before Day 168, then the patient will discontinue the study drug. The End-of-Treatment Visit evaluations will be completed on the day of progression and patient will enter the safety Follow-up Phase.

4.1.3 End-of-Treatment Visit (EOT)

An End-of-Treatment Visit will be scheduled on Day 170 (Visit 8) of the study. All patients who will complete the Treatment phase will be assessed for EOT. In the event where a patient discontinues the study treatment for any reason listed in Section 7.1 before Day 168, the last visit of the patient will be considered as the End-of-Treatment Visit and the patient will be assessed as per EOT visit.

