1. PROTOCOL SUMMARY

1.1 Schedule of Activities (SoA)

Table 1: Schedule of Activities (SoA)

Study Phase	Screening Phase	Treatment Phase ^a		Follow-up Phase
Cycle		Cycles 1-6	EOT	EOS
Visit No.	1	2-7 (Day 1 of each cycle)	8	
Study Days	-6 to 0	1-168 (28 days per cycle)	170	28 days post-EOT
Screening/Enrolment visit				
Informed consent ^s	X			
Eligibility Criteria	X			
Demographics/ Review medical history	X			
ECOG Performance Status	X	X	X	
General Physical examination ^b	X	Symptom-directed physical examination only		
Concomitant medication recording	Continuous from the time of ICF until 28 days after the last Acalabrutinib dose in the treatment phase.			
Study Drug Administration				
Acalabrutinib dosing		The recommended dose is Acalabrutinib 100 mg capsules BID, starting on Day 1 Cycle 1, until disease progression or unacceptable toxicity. Each cycle of treatment is 28 days.		
Disease Evaluations (Disease characteristics will be performed as per routine clinical practice)				
Baseline Disease Characteristics	X			
Safety Evaluations (baseline and each treatment visit) [*]				
Physical examination ^b	X	Symptom-directed physical examination only		
Vital parameters ^c	X	X	X	
Adverse event monitoring	Continuous from the time of ICF until 28 days after last study dose of Acalabrutinib.			

Study Phase	Screening Phase	Treatment Phase ^a		Follow-up Phase
Cycle		Cycles 1-6	EOT	EOS
Visit No.	1	2-7 (Day 1 of each cycle)	8	
Study Days	-6 to 0	1-168 (28 days per cycle)	170	28 days post-EOT
12-lead ECG	X	X	X	
Lymph node biopsy ^d	X			
Next-generation sequencing (NGS)-CLL panel ^e	X			
Haematology ^f & Biochemistry ^g	X	X	X	
Urinalysis ^h	X	X	X	
Pregnancy Test ⁱ	X	X	X	
Chest X-ray ^j	X	X	X	
Efficacy Evaluations (once in 3 months)				
CT/MRI ^k	X	X	X	
EORTC QLQ-C30 Questionnaire	X	X	X	

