4.1.4 Follow-Up Phase (End-Of-Study)

The Follow-up Phase will begin once a patient discontinues study drug or completes the Treatment Phase. The follow-up phase will continue until 28 days after last dose, loss to follow up, withdrawal of consent for study participation, or end of the study, whichever occurs earlier. A follow-up will be conducted 28 days after the EOT visit via a phone call. This will be considered as End-of-Study Visit. Every effort should be made to conduct the End-of-Study Visit.

Patients who are observed to receive clinical benefit from Acalabrutinib after completion of treatment phase, may continue to receive Acalabrutinib, if in the opinion of their treating physician they are continuing to derive clinical benefit from continued treatment or have not progressed clinically. The details on “Post-Trial Access” are provided in section 1.2.

For details on treatments given during the study, refer Section 6.1 Treatments Administered.

For details on what is included in the efficacy and safety endpoints, refer Section 3 and 8.

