8.2.2 Time period and frequency for collecting AE and SAE information

Adverse events and SAEs will be collected from the time of signature of informed consent, throughout the treatment period (168 days), End of study visit (Day 170) and including the follow-up period (28 days after the last dose of study drug) in patients who discontinue before 168 days.

If a patient discontinues from study drug for reasons other than disease progression, drug-related SAEs must be captured until the patient is initiated on an alternate intervention or up to 28 days, whichever is earlier.

All SAEs will be recorded and reported to the Sponsor or designee within 24 hours, as indicated in Appendix B. The Investigator will submit any updated SAE data to the Sponsor within 24 hours of it being available.

Investigators are not obligated to actively seek AE or SAE in former study patients. However, if the Investigator learns of any SAE, including death, at any time after a patient's last visit and he/she considers the event to be reasonably related to the study treatment or study participation, the Investigator may notify the Sponsor.

The method of recording, evaluating, and assessing causality of AE and SAE and the procedures for completing and transmitting SAE reports are provided in Appendix B.

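### Protocol 4.1.3 does not date the End-of-Treatment visit after an early stop, and the only follow-up call is timed from that visit instead of from the last dose

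*Protocol*

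**What the plan says.** Four parts of the protocol bear on this.

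- **EOT visit, Section 4.1.3.** For completers: "An End-of-Treatment Visit will be scheduled on Day 170 (Visit 8) of the study". For a stop before Day 168 for any Section 7.1 reason: "the last visit of the patient will be considered as the End-of-Treatment Visit and the patient will be assessed as per EOT visit". Disease progression is one of the Section 7.1 reasons.
- **Progression, Section 4.1.2.** If progression is diagnosed before Day 168: "The End-of-Treatment Visit evaluations will be completed on the day of progression and patient will enter the safety Follow-up Phase".
- **Follow-up, Section 4.1.4.** The phase has one anchor: "The follow-up phase will continue until 28 days after last dose", or an earlier listed end such as loss to follow-up. The contact has another: "A follow-up will be conducted 28 days after the EOT visit via a phone call". That call is the End-of-Study visit, and the Schedule of Activities (SoA) likewise counts it from EOT.
- **Adverse event window.** The SoA sets monitoring as "Continuous from the time of ICF until 28 days after last study dose of Acalabrutinib". Section 8.2.2 describes collection as "including the follow-up period (28 days after the last dose of study drug) in patients who discontinue before 168 days".

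The SoA has no early-termination column, and no section gives a window between last dose and EOT for stops other than progression. Section 8.2.2 also calls Day 170 the end-of-study visit, whereas 4.1.3 calls it EOT.

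**The concern.** The early-stop clause in 4.1.3 deems a visit to be EOT; it does not tell the site to schedule one. Clinic visits are 28 days apart, so a patient who stops between visits and does not return has no visit after the stop to which the clause can apply. A site that takes the words literally would then use the preceding cycle visit. With ten sites planned, the rule may be applied in different ways.

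The two anchors turn this into a question of safety capture. The call counts from EOT and the adverse event window counts from the last dose, so an EOT dated before the last dose puts the only scheduled follow-up contact inside the window. Under Section 4.4 a patient has completed the study at the last scheduled visit, and Section 8.2.2 does not oblige investigators to seek events actively in former patients. Events between the call and the end of the window would then depend on spontaneous reporting. Adverse events and reasons for discontinuation are the primary outcome, and early stoppers are the patients in whom this matters most.

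**Working it through.** **Inputs**

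- Cycle length 28 days, six cycles (SoA; Section 4.1.2). Check of the plan's own figure: 6 × 28 = 168 days, as stated.
- Visits on Day 1 of each cycle (SoA): 1 + 28 × (c − 1) for c = 1 to 6, giving Days 1, 29, 57, 85, 113 and 141.
- Completers' EOT on Day 170 (4.1.3).
- Call at EOT + 28 (4.1.4; SoA).
- Adverse event window closing at last dose + 28 (SoA; 8.2.2).

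Visits are taken at their nominal days.

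**Completers.** Call on 170 + 28 = Day 198, which is 198 − 168 = 30 days after the last dose. The two anchors already differ by two days here, without harm.

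**Reading A: EOT is the last scheduled visit already made.** Let d be the last-dose day (1 to 167) and v the latest visit day not after d.

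- Gap from EOT to last dose: g = d − v. It runs from 0 to 27 in Cycles 1 to 5 and from 0 to 26 in Cycle 6.
- Interval from last dose to call: (v + 28) − d = 28 − g. Range 1 to 28 days.
- The interval equals 28 only when the last dose falls on a visit day, which is six days. It is shorter for 167 − 6 = 161 of 167 possible days (96.4%).
- Mean gap if last-dose days are spread evenly: (5 × 378 + 351) / 167 = 2241 / 167 = 13.4 days. Mean interval to the call: 28 − 13.4 = 14.6 days.

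| Last dose | EOT | Call | Days from last dose to call | Window closes |
|---|---|---|---|---|
| Day 105 | Day 85 | Day 113 | 8 | Day 133 |
| Day 112 | Day 85 | Day 113 | 1 | Day 140 |
| Day 167 | Day 141 | Day 169 | 2 | Day 195 |

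**Reading B: EOT is held m days after the last dose, m ≥ 0.** The interval from last dose to call is 28 + m: 28 days for m = 0, 30 for m = 2, 35 for m = 7 (2 and 7 are illustrative). It is never below 28.

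The whole shortfall therefore depends on which visit is taken as EOT. Timing the call from the last dose removes it under either reading.

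**The case against.** The strongest reply is that Section 4.1.3 does not say that the visit is one already made. Its closing clause says the patient will be assessed as for EOT, which looks forward. Other text agrees: 4.1.2 dates the evaluations on the day of progression, 7.2 refers to data collected at the time of discontinuation, and the pregnancy-test text in 8.1.2 names an early termination visit. This stands, and it makes Reading B the more natural intention. It does not remove the ambiguity, because no section gives the early visit a date for reasons other than progression.

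Three stronger inferences are tempting, and the documents do not support them.

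- **Early stoppers have no data after the stop.** Section 8.1.2 requires repeat tests for Grade 3 or 4 laboratory values present at discontinuation from the study, with an exception for underlying disease, and provides for ECGs when clinically indicated. Section 8.2.3 requires follow-up of unresolved events.
- **An early call shortens the adverse event window.** On paper it does not. The window is stated separately from the last dose, so an early call conflicts with it without replacing it. Sections 7.1 and 8.2.2 also let follow-up, or capture of drug-related serious events, end sooner if another therapy starts. For those patients 28 days is an upper limit.
- **Visit 8 summaries are biased favourably.** No SAP text maps an early EOT to Visit 8, and 4.1.3 attaches Visit 8 to Day 170. SAP Table 14.2.1 gives Visit 5 its own rows and bases percentages on all patients in the group, so a patient without a Visit 8 assessment already stays in the denominator.

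**Conclusion.** The point holds as a conflict in timing rules that needs to be reconciled. Section 4.1.3 states a rule for every early stop that can be read as relabelling a visit made before the stop. It overlaps 4.1.2 for progression and leaves other reasons undated. The only scheduled follow-up contact is tied to that visit, while follow-up and adverse event collection are tied to the last dose.

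The size is conditional. Under Reading A the call comes 1 to 28 days after the last dose and is short of 28 days for 161 of 167 possible last-dose days. The mean of 14.6 days further assumes evenly spread last-dose days, for which the documents give no basis. Under Reading B the call is never short. The documents do not say how many patients will stop between visits without returning, so the number affected cannot be estimated.

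The change is worth making because it protects capture of the primary safety outcome under both readings.

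**What to change.** - **Protocol 4.1.2 and 4.1.3:** define the early EOT visit as a visit held at or after the decision to stop treatment, for every Section 7.1 reason, with one rule covering progression. Bring 7.2 and the early termination visit in 8.1.2 into line with it.
- **Protocol 4.1.4 and the SoA:** time the End-of-Study call from the last dose, so that it is not made before the 28-day adverse event window closes.
- **Protocol 8.2.2:** use the same names for Day 170 and the End-of-Study contact as 4.1.3 and 4.1.4.
- **SAP:** add one sentence stating that a visit made before discontinuation is not reported as Visit 8. The denominator of Table 14.2.1 needs no change.

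The cost is wording in two documents and, where a patient stops between visits, one visit whose assessments are already in the EOT column of the SoA. No new procedure is needed.
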